### 1.2.3.2 Clinical Study in COVID-19

A randomized, double-blinded, clinical study of GT0918 was done in Brazil for both male and female subjects with mild or moderate COVID-19 illness (NCT04446429). Two hundred and sixty-two (262) men were included in the study. 134 men were assigned to the GT0918 group and 128 men were assigned to the control group. The mean age was 44.5±7.7 years old. Thirty-five subjects (27%) were hospitalized in the control group compared to 0 patients in the GT0918 group by Day 30. The proportion of COVID-19 subjects hospitalized was significantly different between the GT0918 and control arms;  $p<0.0001$ . No subject receiving GT0918 died compared to 2% in the control group. Additionally, it also showed a clinical meaningful SARS-CoV-2 viral load reduction and clearance in the GT0918 group compared to the placebo group (RT-PCR positive rate: 42.5% vs 93.8% on Day 7, 15.0% vs 56.2% on Day 14 and 10.0% vs 43.8% on Day 28, respectively).

Treatment-emergent adverse events were reported for 34% of subjects in the GT0918 group and for 61% of subjects in the placebo group. SAEs were only reported in the placebo group. There was no AE leading to discontinuation.

The most frequently reported TEAEs (occurring in  $\geq 10\%$  of subjects) were diarrhea (21%), dehydration (15%), nausea (14%), abdominal pain (12%), dyspepsia (11%) and back pain (10%) in the GT0918 group. The most frequently reported TEAE were disease progression (54%), fatigue (45%), shortness of breath (36%), fever (20%), dehydration (14%), anosmia (13%), ageusia (12%), back pain (12%), and ear pain (10%) in the placebo group. Gastrointestinal TEAE were more frequent in the GT0918 group. General, respiratory, and nerve system TEAEs are more frequent in the placebo group. The TEAEs suspected to be related with study treatment ( $\geq 10\%$ ) were diarrhea, nausea, abdominal pain and dyspepsia in the GT0918 group. No SAE was reported in the GT0918 group. Acute respiratory distress syndrome was reported as SAE in 27% of the subjects in the placebo group.

178 female subjects were randomized to the study with 76 in the GT0918 group and 102 in the control group. All subjects were also treated with the standard of care.

The mean age was 44.2 years old. Nineteen subjects (19%) were hospitalized in the control group compared to 2 patients (3%) in the GT0918 group by Day 30. ( $p<0.0001$ ). No subject receiving GT0918 died compared to one (1%) in the control group.

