Characterize the pharmacokinetics of GT0918	
 
Mean trough concentration of GT0918 and GT0955 on Days 1, 3, 7 and 14
 
To explore relationships between GT0918 and/or GT0955 exposure and selected efficacy and safety endpoints and/or biomarkers
 

Characterize emergence of viral resistance to GT0918	Screening for novel mutants in patients who do not respond to GT0918 

• Genotype of SARS-CoV-2 viral isolates

To explore biomarkers predictive of GT0918 safety, efficacy, and/or disease progression and COVID-19 clinical outcomes	The association between changes in disease related biomarkers with clinical endpoints

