### **7.2.8 Development of resistance**

Characterize emergence of virus resistance to GT0918

- Virus load assessment on Day -1/1(baseline prior to first dose), 3, 7, 14, 28.
- Exploratory endpoints will include:
  - Screening for novel mutants in patients who do not respond to GT0918:
    - Genotype of SARS-CoV-2 viral isolates.

For resistance analyses, include subjects who:

- Are not able to show two consecutive negative test results via RT-PCR testing by Day 28,  
and/or
- Show a positive real-time RT-PCR test result after two consecutive negative RT-PCR test results,  
and/or
- A confirmed rise in SARS-CoV-2 RNA of  $\geq 1$  log10 after achieving nadir on treatment.

Characterize emergence of host resistance to GT0918

- Testosterone levels on Day -1, 3, 7, 14, 28.

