### **10.6.2 Viral resistance to GT0918**

If appropriate, the evaluation of viral resistance will be conducted as described in a separate bioanalytical analysis plan. Comparison from baseline to the last evaluable time point up to Day 28 on the emergence of viral resistance to GT0918.

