If a patient has not experienced SARS-CoV-2 clearance by completion or early discontinuation of study/study treatment, the patient will be censored at the date of their last visit during the post-treatment period.

Time to SARS-CoV-2 clearance will be applying the same KM methods and Cox proportional hazard models introduced for the time to sustained 100% SARS CoV-2 viral reduction analysis.

Viral Load AUC

SARS-CoV-2 viral load area under the concentration-time curve (AUC) will be calculated according to the linear trapezoidal rule using the measured SARS-CoV-2 viral load-time values above the lower limit of quantification (LoQ) at Days 3, 7, 14 and 28. Per ICON central lab, LoQ is 59.9 copies/mL. No imputations of missing data will be conducted. No AUC(0-D28) values will be calculated when Day 1 pre-dose and/or Day 28 values are missing, or if there are more than 3 values missing in the profile. The AUC (0-D28) will be summarized and plotted by treatment group and listed.

Viral Resistance by Day 28

The proportion of viral resistance at day 28 will be summarized by treatment group and listed. The CMH chi-square test introduced for the primary endpoint analysis will be used to compare the difference of proportion of viral resistance between treatment groups by day 28.

Viral resistance is defined as when subjects:

- Are not able to show two consecutive negative test results via ddPCR testing by Day 28 without any missing scheduled tests, and/or

- Show a positive real-time ddPCR test result after two consecutive negative ddPCR test results, and/or
- A confirmed rise in SARS-CoV-2 RNA of ≥ 1 log10 after achieving nadir on treatment.

COVID-19 Ordinal Outcomes Scale

Below summaries will be provided using mITT set:

- The percentage of subjects at each clinical status using NIAID 8-point ordinal scale at Days 3, 7, 14, and 28

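### SAP 4.10.3 turns the protocol's rule for choosing subjects for resistance analyses into the definition of viral resistance and tests it between arms, so the test measures late clearance or rebound rather than resistance to GT0918.

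*SAP*

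**What the plan says.** **Protocol.** Section 3 makes emergence of viral resistance to GT0918 an exploratory objective, with the endpoint "Genotype of SARS-CoV-2 viral isolates". Section 7.2.8 repeats it as "Screening for novel mutants in patients who do not respond to GT0918". It then gives three criteria joined by and/or, introduced by "For resistance analyses, include subjects who". The first is "Are not able to show two consecutive negative test results via RT-PCR testing by Day 28". The second is a positive result after two consecutive negatives, and the third is a confirmed rise of at least 1 log10 in viral RNA after the on-treatment nadir. Section 10.6.2 says that, if appropriate, "the evaluation of viral resistance will be conducted as described in a separate bioanalytical analysis plan". It names a comparison of baseline with the last evaluable time point and no test between arms.

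**SAP.** Sections 2.3 and 3.3.3 keep resistance to GT0918, mutant screening and genotype as exploratory. Section 4.10.3, under secondary efficacy, has a paragraph on viral resistance by Day 28. It summarises the proportion by treatment group, compares the groups with the CMH test of the primary endpoint, and gives the definition: "Viral resistance is defined as when subjects", followed by the protocol's three criteria. The first now reads "Are not able to show two consecutive negative test results via ddPCR testing by Day 28 without any missing scheduled tests", and the assay is ddPCR throughout. Section 4 describes no analysis of genotype.

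Protocol 10.1 says that the SAP prevails where the two documents differ.

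**The concern.** In the protocol the criteria say which subjects enter the resistance analyses. In the SAP, meeting them is resistance. Nothing in the SAP definition calls for a mutation, a comparison with the baseline isolate, or exposure to GT0918, so it applies equally to both arms. A placebo subject with slow clearance counts as a case of resistance to a drug that the subject did not receive.

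At stake is the interpretation of a named, though exploratory, objective. A difference between arms on this outcome would reflect how quickly virus clears, which is efficacy. Equal proportions would say nothing about resistance either.

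**Working it through.** The documents give no figure for this outcome to reproduce. The check compares the texts and then works out what the SAP definition counts.

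**1. The two texts**

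| | Protocol 7.2.8 and 10.6.2 | SAP 4.10.3 |
|---|---|---|
| Role of the three criteria | entry to the resistance analyses | definition of the outcome |
| Genotype needed | listed as the endpoint | no |
| Exposure to GT0918 needed | screening is in non-responders to GT0918 | no |
| Comparison | baseline with last evaluable time point | GT0918 with placebo, CMH test |
| Missing swabs | not mentioned | criterion 1 requires all scheduled tests |

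**2. What criteria 1 and 2 count**

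Input: scheduled post-baseline swabs at Days 3, 7, 14 and 28 (Schedule of Activities in both documents), none missing. Each is positive (P) or negative (N), which gives 2 × 2 × 2 × 2 = 16 patterns. Criterion 1 is met if no two adjacent results are both N. Criterion 2 is met if a P follows two adjacent Ns.

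| Day 14 / Day 28 | Patterns (Days 3, 7, 14, 28) | Criterion met |
|---|---|---|
| N / N | NNNN, NPNN, PNNN, PPNN | neither |
| N / P | NPNP, PPNP | 1 |
| N / P | NNNP, PNNP | 2 |
| P / N | NPPN, PNPN, PPPN | 1 |
| P / N | NNPN | 2 |
| P / P | NPPP, PNPP, PPPP | 1 |
| P / P | NNPP | 2 |

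Flagged: 16 − 4 = 12 patterns. The four that escape are exactly those negative on both Day 14 and Day 28. Criterion 3 can only add subjects. Its reference to a nadir on treatment does not remove placebo subjects, because the proportion is tabulated and tested by arm.

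Hence, among complete-swab subjects in either arm,

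flagged proportion ≥ proportion positive at Day 14.

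Under criteria 1 and 2 alone, equality holds if no one positive at Day 28 was negative at Day 14.

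**3. Overlap with clearance**

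SAP 4.10.3 separately defines viral clearance by at least two consecutive negatives. Criterion 1 is close to the complement of clearance by Day 28, so the comparison largely repeats an analysis that the SAP already has under its proper name.

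**4. Illustration of size (assumption, not a forecast)**

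Protocol 1.2.3.2 reports positivity of "15.0% vs 56.2% on Day 14" (GT0918 vs placebo) in the paragraph on the male cohort of the earlier study. If complete-swab subjects here had those rates:

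- floor on placebo 56.2%, floor on GT0918 15.0%, difference 56.2 − 15.0 = 41.2 percentage points;
- odds ratio if the proportions equalled the floors: (0.562 / 0.438) / (0.150 / 0.850) = 1.283 / 0.1765 ≈ 7.3, with the higher odds of being called resistant in the placebo arm.

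**5. Direction of the test**

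The borrowed CMH test is one-sided at 0.025 with alternative p1 − p2 > 0, where a higher proportion is favourable (SAP 4.10.1). A higher proportion meeting the resistance criteria is unfavourable. SAP 4.10.3 does not restate the direction.

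**The case against.** Much can be said for the plan, and several stronger readings should be set aside.

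- *That 56.2% and 15.0% are what this trial will show.* The documents do not support this. The rates come from one male cohort and an RT-PCR assay, whereas the SAP uses ddPCR. Their denominator is not stated and cannot be the 134 men on GT0918, since 20/134 = 14.9% and 21/134 = 15.7%. Outcome rates also differ: SAP 4.10.1.1.3 reports under two percent hospitalization here, against 27% in that placebo group. The floor applies only to subjects with complete swabs.
- *That the genotypic analysis has been lost.* This is not shown. Protocol 10.6.2 assigns the evaluation to a separate plan that is not available here, and SAP 3.3.3 keeps the genotype endpoint. What is shown is an additional, mislabelled analysis.
- *That resistance has been promoted to a secondary endpoint.* It is exploratory in SAP 2.3 and 3.3.3 and absent from the secondary list in 3.3.2. Only its position under 4.10.3 is inconsistent.
- *That the SAP created the case of a subject whose first negative is at Day 28.* That follows from the protocol's own wording and last swab. It is tolerable in a selection rule and matters only once the rule becomes the outcome.
- *That placebo subjects should not appear at all.* Including them is not the error. Without them, drug-driven mutation cannot be told from natural drift.
- *That the sponsor will report less resistance with the drug.* The SAP specifies a summary, a listing and a test. It does not say what will be concluded.

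The outcome has no alpha of its own, and clearance is analysed openly elsewhere. These points limit the consequence. They do not rescue the definition, which governs because the SAP prevails over the protocol and which needs neither genotype nor drug exposure.

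**Conclusion.** The point holds: the analysis is wrong as written, with low impact. Among subjects with all four post-baseline swabs, the SAP counts as resistant everyone who is not negative on both Day 14 and Day 28, whichever treatment was taken. The between-arm test therefore compares late clearance or rebound and does not address emergence of resistance to GT0918.

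This conclusion rests on the wording of the two documents and the enumeration of patterns, not on any assumed rate. The size in this trial is unknown; the earlier study's percentages only show that the flagged proportions could be large and higher on placebo. The primary conclusion is unaffected.

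**What to change.** In SAP 4.10.3:

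1. Rename the composite *virologic non-clearance or rebound* and place it with the exploratory analyses, in line with 2.3 and 3.3.3.
2. If the between-arm CMH test is kept, state its direction for an unfavourable outcome, and say whether subjects with missing swabs leave the denominator or count as not flagged.
3. For resistance itself, use the three criteria only to select subjects for the resistance analyses, as in protocol 7.2.8.
4. Reserve *resistance* for treatment-emergent genotypic change from the baseline isolate, with a cross-reference to the bioanalytical plan in protocol 10.6.2. Report flagged placebo subjects alongside as the background mutation rate.

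The cost is SAP wording. Genotype of isolates is already a listed endpoint, and the change needs no new visit or swab. Whether the bioanalytical plan already covers flagged placebo subjects should be checked.

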3.3.2 Secondary

Hospitalization Percentage

- Percentage of subjects who experience any of the following events due to all causes by Day 28:
 - Hospitalization for \geq 24 hours or
 - Supplemental oxygen for \geq 24 hours in response to SpO₂ \leq 93% or
 - Death

Virologic Response

- Change from baseline to Days 3, 7, 14 and 28 in SARS CoV-2 viral load
- Proportions of subjects that achieve sustained 100% SARS-CoV-2 viral reduction at Days 3, 7, 14 and 28
- Time to sustained 100% SARS-CoV-2 viral reduction
- Proportion of subjects that achieve SARS-CoV-2 clearance (Days 3, 7, 14 and 28)
- Time to SARS-CoV-2 clearance
- SARS-CoV-2 viral load area under the concentration-time curve (AUC) assessed to days 3, 7, 14 and 28

NIAID Ordinal Scale

- Percentage of subjects achieving each clinical status at Days 3, 7, 14 and 28 as defined below based on The National Institute of Allergy and Infectious Diseases (NIAID) 8- point ordinal scale
 - 1 Death
 - 2 Hospitalized, on invasive mechanical ventilation or extracorporeal membrane oxygenation (ECMO)
 - 3 Hospitalized, on non-invasive ventilation or high flow oxygen devices
 - 4 Hospitalized, requiring supplemental oxygen
 - 5 Hospitalized, not requiring supplemental oxygen - requiring ongoing medical care (COVID-19-related or other medical conditions preventing hospital discharge)
 - 6 Hospitalized, not requiring supplemental oxygen - no longer requires ongoing medical care
 - 7 Not hospitalized, limitation on activities and/or requiring home oxygen
 - 8 Not hospitalized, no limitations on activities
- Proportion of subjects with all-cause hospitalization (defined as \geq 24 hours) by Day 28
- Proportion of subjects with COVID-19 related hospitalization (defined as \geq 24 hours) by Day 28
- Days of hospitalization due to all causes or COVID-19 by Day 28
- Time to hospitalization due to all causes or COVID-19 by Day 28
- Proportion of subjects requiring supplemental oxygen, high-flow oxygen, any ventilation or ECMO due to COVID-19 by Day 28

Symptom Questionnaire

- Symptom Improvement:
 - Change in symptom score (total of ratings) from baseline to Days 3, 7, 14 and 28
 - Time to symptom improvement

- Proportion of subjects demonstrating symptom improvement via the symptom questionnaire (total of ratings) on Days 3, 7, 14 and 28
- Symptom Resolution:
 - Proportion of subjects demonstrating symptom resolution via the symptom questionnaire on Days 3, 7, 14 and 28
 - Time to symptom resolution

Safety

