- Comparison of the proportion of NIAID ordinal scale by Days 3, 7, 14, and 28: ordinal generalized estimating equation (GEE) with treatment, age, stratification factors (sex, race and ethnicity, and number of risk factors), visit, and interaction of visit and treatment will be included in the model as fixed effects, and subject will be included as a random effect. Odds ratios with 95% confidence intervals and p-values will be presented. If data are too sparse for one level of the above factors, the factor will not be included in the statistical model/test to avoid convergence issue. Inferential analysis will only be performed if data warrants.
- Proportion of subjects worsening from baseline (worsening is defined as any worsening on the NIAID ordinal scale from baseline to Days 3, 7, 14, and 28)

Stacked bar plot by treatment group and visits at Day 1, 3, 7, 14 and 28 will be produced for NIAID ordinal scale. Also, mean value by treatment group will be plotted over time.

All NIAID ordinal scales through the study period will be listed in listing.

Other Analysis for Clinical Status

Below summaries for other analysis for clinical status will be provided as well:

- Summary of Hospitalization and Extended Care Facility Admissions by Day 28 (COVID-19 related will be summarized separately)
Note: Hospitalization (≥ 24 hours) includes: Hospitalization, Emergency room and ICU. Extended Care Facility Admittance is excluded.
 - Number and proportion of subjects hospitalized
 - Duration of Hospitalization
 - Number and proportion of subjects hospitalized by admission type: Hospitalization, Emergency Room, Intensive Care Unit (ICU) and Extended Care Facility
 - Duration by admission type
 - Comparisons of proportion of hospitalization between treatment group will be made using FIRTH logistic regression, with adjusting age and the stratification factors (sex, race and ethnicity, and number of risk factors). Odds ratios with 95% confidence intervals and p-values will be present. If data are too sparse for one level of the above factors, the factor will not be included in the statistical model/test to avoid convergence issue. Inferential analysis will only be performed if data warrants.
- Summary of New Oxygen Use by Day 28 (COVID-19 related will be summarized separately)
 - Number and proportion of subjects requiring any oxygen use
- Summary of COVID-19 Related Medical Attended Visits by Day 28
 - Proportion of subjects with COVID-19 related medical attended visits

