
All hospitalization events and COVID-19 related medical attended visits will be listed.

Time to Hospitalization

Time to Hospitalization (in days) is defined as:

First hospital admission date - first dosing date + 1.

Note: Hospitalization (≥ 24 hours) includes Hospitalization, Emergency room and ICU. Extended Care Facility Admittance is excluded.

The following two summaries will be generated separately:

- All-Cause Hospitalization
- COVID-19 Related Hospitalization

If a patient has not experienced hospitalization by completion or early discontinuation of study/study treatment, the patient will be censored at the date of their last visit during the post-treatment period.

Time to hospitalization will be evaluated up to Day 28 and will be summarized and plotted by treatment group with mITT set using the Kaplan-Meier (KM) method. The 2-sided 95% CIs for the 25th, 50th and 75th percentiles, as well as at days 3, 7, 14 and 28 using the Brookmeyer and Crowley method will be reported when estimable. P-value will be obtained from the log-rank test stratified by age, and sex, race and ethnicity, and number of risk factors at randomization. Hazard ratios and corresponding 95% confidence intervals will be obtained from a Cox proportional hazard model which treated treatment group as a unique covariate, and age, and sex, race and ethnicity, and number of risk factors as stratas. The Cox proportional hazard model will be also performed by subgroup of duration since symptom onset to randomization category (≤ 3 days; > 3 days).

If cases of hospitalization are too sparse (e.g., < 1 case in one treatment group), no time to hospitalization analyses will be performed.

Proportion of Symptom Resolution

All symptom resolution is defined as

all symptoms (those scored 0-3*) on the symptom questionnaire scored as absent (scored 0), with each symptom resolution absent for at least 48 hours.

Note: * Seven individual questions from COVID-19-Related Symptom Questionnaire are included here: questions 3, 4, 5, 6, 7, 8 and 9.

Additionally, all symptom resolution will be defined differently to include all individual questions scored 0-3 and related outputs will be noted as sensitivity analysis. It is defined as

all symptoms (those scored 0-3*) on the symptom questionnaire scored as absent (scored 0), with each symptom resolution absent for at least 48 hours.

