4.12 Determination of Sample Size

The primary endpoint event rate for the treatment arm is assumed at 97% and for the placebo arm is assumed at 91%.

The sample size was calculated using EAST v6.5 software for a group sequential test for 2 proportions. With a total of 668 subjects the study will have about 90% power at a one-sided 0.025 significance level of the hospitalization or death rate using a Chi-square test with one interim analysis at 50% of the information (when 334 subjects have been observed for 28 days).

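### SAP 4.10.3 drops every time-to-hospitalization analysis when one arm has no cases, although only the ordinary Cox hazard ratio fails

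*SAP*

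**What the plan says.** SAP 3.3.2 lists the endpoint among the secondary ones: "Time to hospitalization due to all causes or COVID-19 by Day 28". SAP 4.10.3 then plans three analyses, each for all-cause and for COVID-19 related hospitalization:

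- Kaplan-Meier: "Time to hospitalization will be evaluated up to Day 28 and will be summarized and plotted by treatment group with mITT set".
- Log-rank: "P-value will be obtained from the log-rank test stratified by age, and sex, race and ethnicity, and number of risk factors at randomization".
- Cox: "Hazard ratios and corresponding 95% confidence intervals will be obtained from a Cox proportional hazard model", with the same factors as strata.

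The section closes with the sparse-data rule: "If cases of hospitalization are too sparse (e.g., < 1 case in one treatment group), no time to hospitalization analyses will be performed". No substitute time-to-event method is named.

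A few paragraphs earlier, the same section treats sparse hospitalization proportions differently: "Comparisons of proportion of hospitalization between treatment group will be made using FIRTH logistic regression". There, factors with sparse levels are dropped from the model, and inference is made conditional on the data supporting it.

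**The concern.** The rule is wider than the problem it addresses. With no events in one arm, that arm's Kaplan-Meier curve is a flat line at 1, and the log-rank statistic compares observed with expected events as usual. Only the ordinary Cox estimate runs to zero or infinity. The same paragraph already shows a narrower approach, since it reports the percentile limits only where they can be estimated.

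The trigger also depends on the split of events between arms, and it is given only as an example. The actual threshold is therefore open and could be settled after the results by arm are known. At stake is a SAP-listed secondary analysis that would go missing for a split such as 0 against 9 in either direction.

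**Working it through.** **The plan's own figure.** SAP 4.12 states: "The primary endpoint event rate for the treatment arm is assumed at 97% and for the placebo arm is assumed at 91"%, with 668 subjects for about 90% power at one-sided 0.025. The fixed-sample formula, with mean proportion 0.94 and difference 0.06, is n per arm = [1.960·√(2·0.94·0.06) + 1.2816·√(0.97·0.03 + 0.91·0.09)]² / 0.06² = (0.658 + 0.427)² / 0.0036 ≈ 327.2, rounded up to 328, or 656 in total. With the O'Brien-Fleming-type interim at half the information, power at 668 is 90.3% (pooled variance). The design reproduces, with 334 per arm.

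**Chance of a zero arm.** For true rate p, P(no events among 334) = (1−p)^334. If both arms share that rate, the rule fires with probability 1 − [1 − (1−p)^334]². Apart from the 3% design rate, the documents give no arm-level rates for this trial, so the rates are assumptions shown as a range.

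| True rate | P(no events in a given arm) | P(rule fires, same rate in both arms) |
|---|---|---|
| 3% (design rate on drug, composite) | 0.004% | not applicable |
| 2% | 0.1% | 0.2% |
| 1% | 3.5% | 7% |
| 0.5% | 19% | 34% |
| 0.25% | 43% | 68% |

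With unequal rates, the rule fires 19% of the time at 0.5% against 2%, and 43% at 0.25% against 1.75%.

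**Why low rates matter here.** SAP 4.10.1.1.3 says that less than two percent hospitalization was observed. Since 0.02 × 668 = 13.4, that is at most 13 cases over both arms. COVID-19 related cases cannot outnumber all-cause cases, so a zero arm is at least as likely for that version.

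**What could still be reported at 0 against k events.** Take 334 per arm, no stratification and risk sets staying close to 1:1.

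- Log-rank: z = (k/2) / √V, with V the sum of n₀n₁/(n₀+n₁)² over the k event times. For k = 9, z = 4.5 / √(9·659/(4·667)) = 3.02.
- Exact upper limit (one-sided 97.5%): solve (1/(1+HR))^k = 0.025, giving HR = 40^(1/k) − 1.
- Ordinary profile upper limit (95%): HR = exp(3.8415/(2k)) − 1.
- Firth: the penalised log-likelihood is 0.5·ln HR − (k+1)·ln(1+HR). Its maximum is at HR = 0.5/(k+0.5), and the limits lie where twice the drop from the maximum equals 3.8415.

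| Split | Log-rank one-sided p | Fisher one-sided p | Firth HR | Firth upper | Ordinary profile upper | Exact upper |
|---|---|---|---|---|---|---|
| 0 v 1 | 0.159 | 0.500 | 0.33 | 6.2 | 5.8 | 39 |
| 0 v 4 | 0.023 | 0.062 | 0.11 | 1.04 | 0.62 | 1.5 |
| 0 v 6 | 0.0070 | 0.015 | 0.077 | 0.65 | 0.38 | 0.85 |
| 0 v 9 | 0.0013 | 0.0019 | 0.053 | 0.41 | 0.24 | 0.51 |
| 0 v 13 | 0.00014 | 0.00011 | 0.037 | 0.28 | 0.16 | 0.33 |

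Every row is computable, and under the rule none would appear as a time-to-event result. The asymptotic log-rank p-value is too small when events are few: at 0 against 4 it falls below 0.025 while the exact test does not. The unpenalised profile limit is too short in the same way; the Firth limit lies between it and the exact one.

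**The case against.** Several points on the other side stand.

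- **Hospitalization is still analysed.** The one-sided CMH test of the primary composite, the summary of its components, the secondary hospitalization percentage tested in the same way, the counts and durations, and the event listings are all untouched. Firth logistic regression also remains, though only if the data are judged to support it. A 0 against 9 split would be reported and would enter the composite test. What is lost is the timing display, the log-rank test and the hazard ratio.
- **Status.** Time to hospitalization is not in the protocol's endpoint tables, and the SAP's multiplicity section covers only the interim analysis. No confirmatory claim rests on it.
- **A minimum-event rule is legitimate.** This one was written in advance and treats both arms alike. Asymptotic p-values from a handful of events are unreliable, as 0 against 4 shows.

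Two stronger readings are tempting but not supported. A reader might infer that the rule removes the analysis exactly when the treatment effect is largest. It responds to sparsity: it fires on an uninformative 0 against 1, it fires by chance with no effect (7% at 1% in both arms), and it would not fire on 1 against 35. A reader might also infer from the earlier Brazilian study that the rule is likely to apply: "Thirty-five subjects (27%) were hospitalized in the control group compared to 0 patients in the GT0918 group". That is the male cohort only. Protocol 1.2.3.2 also reports 2 of 76 women on drug hospitalized, and this trial enrols both sexes. Pooling gives 2/(134+76) = 2/210 = 0.95%, and (1 − 2/210)^334 = 4%. The under-2% figure in SAP 4.10.1.1.3 makes a zero arm realistic; it does not make it likely.

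These points limit the size of the problem. They do not justify cancelling the curves and the log-rank test because one of three methods fails.

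**Conclusion.** The point holds in a limited form. The rule discards two valid analyses along with the one that fails, and its threshold is left open. The consequence is confined to one SAP-listed secondary time-to-event analysis, in its all-cause and COVID-19 related versions; the primary result and the reporting of hospitalizations do not depend on it.

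The chance that it matters runs from negligible at the design rates to between 3.5% and 43% per arm at assumed true rates between 1% and 0.25%. These figures assume 334 treated subjects per arm with complete follow-up. The p-values and limits are unstratified, whereas the SAP stratifies by age and by 2 × 3 × 3 = 18 randomization cells. The stratified statistic also exists with a zero arm, provided that at least one stratum with an event has subjects at risk in both arms, but its values would differ.

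**What to change.** Delete the sentence that cancels the analyses, together with its open-ended example threshold. In its place:

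1. Always present the Kaplan-Meier curves and the event counts by arm, for all-cause and COVID-19 related hospitalization.
2. When one arm has no events and the other has at least one, replace the ordinary Cox hazard ratio with a Firth-penalised one with profile-likelihood limits. This follows the Firth approach already chosen for the proportion hospitalized.
3. In that case, report the log-rank result with an exact or permutation p-value that respects the strata, rather than the asymptotic one.
4. If neither arm has an event, report the counts only.

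The cost is SAP wording, one model option and slightly more programming. Intervals will be wide when events are few, as they should be. No new data, extra subjects or change to the primary test or its alpha is needed.
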